7.3.3 RANDOMIZATION

Subjects will be randomized after eligibility has been confirmed.

7.3.4 BASELINE: ON-SITE/TREATMENT

The on-site Baseline assessments will be gathered prior to the first infusion on Day 1. After the first infusion on Day 1, the subject will be discharged from the facility and come back the following morning (Day 2) for the inpatient period. The inpatient treatment period is 2 days during which each subject will receive 3 additional doses of 250 mL of their assigned treatment allocation (i.e., either GRF6021 or placebo).

Visits 3 through 5, Treatment (Days 1-3):

- Perform the following procedures on each day *prior* to administering (the first) study infusion:
 - Review AEs and concomitant medications.
 - 12-lead ECG (**Day 1 and 3 Only**).
 - Collect sample for CyTOF assessment (**Including second infusion on Day 2**).

- Obtain samples for proteomic assessments; fasting samples preferred (**Including second infusion on Day 2**).
- Collect vital signs (BP, HR, RR, and body temperature) (**Including second infusion on Day 2**).
- Targeted physical exam (**Day 1 and 3 Only**).
- Pregnancy testing for WOCBP (**Day 1 Only**).
- Administer 3D-CAM, SRS, and WOMAC (**Day 1 and 3 Only**).
- ActiGraph device data collection (**Day 1 and 3 Only**).
- Administer study treatment per the GRF6021 Infusion Administration Manual:
 - On the day before surgery (**Day 1**).
 - On the day of surgery within 4 hours before surgery start (first incision) (**Day 2**).
 - On the day of surgery upon arrival in the PACU (within 5 hours after the first incision) (**Day 2**).
 - On the day after surgery (**Day 3**).
- Perform the following assessments following each infusion start:
 - BP and HR at 15, 30, 45, and 60 min after infusion start.
 - Body temperature and RR at 60 minutes.
 - Collection of perioperative data (**Day 2 Only**, after second infusion).
 - Opioid consumption assessment (**Days 2 and 3 Only**).
 - 12-lead ECG (**Day 3+1 Only**, after end of last infusion).
 - Exit lab panel including pregnancy test (**Day 3 Only**, after end of last infusion).
 - Administer 3D-CAM (**Day 2 Only**, after second infusion).

7.3.5 FOLLOW-UP

All Follow-up Visits will be conducted remotely by phone or electronically.

Visits 6 through 14 (Day 4 through Day 37±2)

- Review AEs and concomitant medications.
- Perform the following assessments:
 - SRS
 - WOMAC
 - Opioid consumption assessment.
- Review AEs and concomitant medications.
- Ongoing collections of data from wearable device.

7.3.6 END OF STUDY VISIT

The End of Study Visit will be conducted remotely by phone and/or electronically.

Visit 15, End of Study (Day 44 ± 2)

- Review AEs and concomitant medications.
- Perform the following assessments:
 - SRS
 - WOMAC
 - SF-36
 - BDI-II
 - Opioid consumption assessment.
- Subject will be instructed to return the ActiGraph wearable device.

7.3.7 EARLY TERMINATION

If a subject has received at least one infusion but is terminated or terminates from the study early, the site should try to perform all assessments scheduled at the End of Study Visit (Visit 15) and complete the exit lab panel if the subject is still at the site and available and willing.

7.3.8 SCHEDULE OF EVENTS TABLE

A tabular summary of all procedures/assessments at each study visit can be found in [Section 15 Schedule of Events](#).

7.4 CONCOMITANT MEDICATIONS

All concomitant prescription medications taken during study participation will be recorded on the CRFs. For this protocol, a prescription medication is defined as a medication that can be prescribed only by a properly authorized/licensed clinician. Medications to be reported in the CRF are concomitant prescription medications, over-the-counter medications, and non-prescription medications. Medications that are considered standard use during surgery will not be collected in the CRF.

7.4.1 ANESTHESIA GUIDELINES

For the purposes of this trial, it is recommended to:

- Avoid adjuvant analgesic techniques that have immune-modulatory potential (e.g. ketamine or IV lidocaine infusions or bolus administration), unless clinically indicated.
- Avoid other medications with immune-modulatory potential such as steroids (e.g. decadron), unless clinically indicated.

7.5 PROHIBITED MEDICATIONS, TREATMENTS, AND PROCEDURES

The following concomitant medications are prohibited:

- Concurrent participation in any other therapeutic treatment trial. If there was prior clinical trial participation, subject must have discontinued investigational agents for at least 30 days for small molecules, and 1 year for active or passive immunotherapies prior to screening.
- Chronic use of anticoagulant therapy (e.g., heparin, warfarin, thrombin inhibitors, Factor Xa inhibitors). Anticoagulation used during surgery is permitted. Use of antiplatelet drugs (e.g., aspirin or clopidogrel) is acceptable.
- Any drugs of the interferon class.
- Systemic corticosteroids (e.g., hydrocortisone, cortisone, betamethasone, prednisone, prednisolone, triamcinolone, dexamethasone, fludrocortisone) for longer than 5 consecutive days. Ophthalmic, topical, intra-articular, and inhaled steroids are allowed.

8 ASSESSMENT OF SAFETY

Assessment of subject safety is the responsibility of the Investigator or medically qualified designee. In extraordinary circumstances where knowledge of whether GRF6021 or placebo was received by a subject is

essential, the Investigator may unblind. Any instances of unblinding will be managed as indicated in [Section 10.6.3 Breaking the Study Blind/Subject Code](#).

8.1 SPECIFICATION OF SAFETY PARAMETERS

8.1.1 DEFINITION OF ADVERSE EVENTS

Per 21 CFR 312.32(a), an AE is any untoward (unfavorable, harmful, or pathologic) medical occurrence in a subject administered a pharmaceutical (investigational) product even if the event does not necessarily have a causal relationship with this treatment.

An AE can therefore be any unfavorable and unintended sign (including an abnormal laboratory finding that is deemed clinically significant), symptom, or disease temporally associated with the use of a medicinal (investigational) product, whether or not related to the medicinal (investigational) product.

An AE does include any:

- Exacerbation of a pre-existing illness.
- Subjective or objective symptoms spontaneously offered by the subject and/or observed by the investigator or study staff.
- Increase in frequency or intensity of a pre-existing episodic event or condition.
- Condition detected or diagnosed after study drug administration even though it may have been present prior to the start of the study (unless it can be demonstrated by medical record review that the onset of the event preceded the date/time of Informed Consent).
- Continuous persistent disease or symptoms present at baseline that worsen following the start of the study.
- Symptoms associated with disease not previously reported by the subject.
- Untoward medical occurrences considered by the investigator to be related to study-mandated procedures.
- Abnormal assessments (e.g., change on physical examination, ECG findings), if they represent a clinically significant finding, that were not present at Baseline or worsened during the course of the study.
- Laboratory test abnormalities, if they represent a clinically significant finding, symptomatic or not, which were not present at Baseline or worsened during the course of the study.

An AE DOES NOT include a/an:

- Elective medical or surgical procedure (e.g., surgery, endoscopy, tooth extraction, transfusion).
- Pre-existing diseases or conditions present or detected at the start of the study that do not worsen.
- Situations where an untoward medical occurrence has not occurred (e.g., hospitalization for cosmetic elective surgery, social and/or convenience admissions).
- The disease or disorder being studied or sign or symptom associated with the disease or disorder unless more severe than expected for the subject's condition.
- Overdose of either study drug or concurrent medication without any signs or symptoms.

- Pregnancy.

8.1.2 DEFINITION OF SERIOUS ADVERSE EVENTS

Note: if either the investigator or the Sponsor believes that the event is serious, the event must be considered serious and evaluated for expedited reporting.

Note: the terms “severe” and “serious” are not synonymous. Severity (or intensity) refers to the grade of an AE. “Serious” is a regulatory definition.

A serious adverse event (experience) or reaction is an untoward medical occurrence that, at any dose, fulfills one or more of the following criteria:

- a. Results in death (i.e., the AE actually causes or leads to death).
- b. Is life-threatening.
 - An AE is considered “life-threatening” if, in the view of either the investigator or Sponsor, its occurrence places the patient or subject at immediate risk of death; it does not include AEs which, had it occurred in a more severe form, might have caused death.
- c. Results in inpatient hospitalization or prolongation of existing hospitalization.
 - Hospitalization for elective treatment of a pre-existing condition that did not worsen during the study is not considered an AE; hospitalization for participating in this study is not considered an AE.
 - Complications that occur during hospitalization are AEs; if a complication prolongs hospitalization, the event is an SAE.
 - “Inpatient” hospitalization means the subject has been formally admitted to a hospital for medical reasons that may or may not be overnight; it does not include presentation at a casualty or emergency room unless the event meets the definition of an Important Medical Event (in the opinion of the Investigator or Sponsor).
- d. Results in persistent or significant incapacity or substantial disruption of the ability to conduct normal life functions.
 - The term ‘disability’ means a substantial disruption of a person’s ability to conduct normal life functions; this definition is not intended to include experiences of relatively minor medical significance such as uncomplicated headache, nausea, vomiting, diarrhea, influenza, accidental trauma (i.e., sprained ankle) that may interfere or prevent everyday life functions but do not constitute a substantial disruption.
- e. Results in a congenital anomaly in the offspring of a subject who received drug.
- f. Results in an Important Medical Event. Important Medical Events are events that may not result in death, be life-threatening, or require hospitalization but may be considered an SAE when, based upon appropriate medical judgment, they may jeopardize the subject and may require medical or surgical intervention to prevent one of the outcomes listed in this definition; examples of such medical events include allergic bronchospasm requiring intensive treatment in an emergency room or at home, blood dyscrasias or convulsions that do not result in inpatient hospitalization, or the development of drug dependency or drug abuse.
 - Medical and scientific judgment should be used in deciding whether prompt reporting is appropriate in this situation.

8.2 CLASSIFICATION OF AN ADVERSE EVENT

8.2.1 SEVERITY OF EVENT

Each AE or suspected adverse reaction must be assessed for its seriousness and severity. Severity will be assessed by the investigator or designee using the following definitions:

SEVERITY	DEFINITION
MILD	Aware of sign or symptom, but easily tolerated
MODERATE	Discomfort enough to cause interference with usual activity
SEVERE	Incapacitating with inability to work or do usual activity

Outcome will be assessed using the following categories: recovered/resolved, not recovered/ not resolved, recovered/resolved with sequelae, fatal, or unknown.

8.2.2 RELATIONSHIP TO STUDY AGENT

Investigators are required to assess the causal relationship (i.e., whether there is reasonable possibility that the study drug caused the event) using the following definitions:

- Unrelated: another cause of the adverse event is more plausible; a temporal sequence cannot be established with the onset of the adverse event and administration of the study agent; or a causal relationship is considered biologically implausible.
- Possibly Related: There is a clinically plausible time sequence between onset of the adverse event and administration of the study agent, but the adverse event could also be attributed to concurrent or underlying disease, or the use of other drugs or procedures. Possibly related should be used when the study agent is one or several biologically plausible adverse event causes.
- Definitely Related: The adverse event is clearly related to use of the study agent.

If either the investigator or the Sponsor considers the event related, then the event will be considered related for reporting purposes.

8.2.3 EXPECTEDNESS

The Sponsor or designee will be responsible for determining whether an AE is expected or unexpected. An AE will be considered unexpected if the nature, severity, or frequency of the event is not consistent with the Reference Safety Information described in the Investigator's Brochure.

For example, under this definition, hepatic necrosis would be unexpected (by virtue of greater severity) if the investigator brochure referred only to elevated hepatic enzymes or hepatitis. Similarly, cerebral thromboembolism and cerebral vasculitis would be unexpected (by virtue of greater specificity) if the Investigator's Brochure listed only cerebral vascular accidents. "Unexpected" as used in this definition, also refers to AEs or suspected adverse reactions that are mentioned in the Investigator's Brochure as occurring with a class of drugs or as anticipated from the pharmacological properties of the drug but are not specifically mentioned as occurring with the particular drug under investigation. For example, although angioedema is anticipated to occur in some patients exposed to drugs in the angiotensin-converting enzyme (ACE) inhibitor class and angioedema would be described in the Investigator's Brochure as a class effect, the first case of angioedema observed with the drug under investigation should be considered unexpected for reporting.

purposes (FDA 2012).

This definition of “unexpected” relies entirely on the Reference Safety Information in the Investigator’s Brochure as the basis for determining if newly acquired information generated from clinical trials or reported from other sources is unexpected. The suspected adverse reactions listed in the Investigator’s Brochure (i.e., “expected”) are those observed with the investigational drug and for which a causal relationship between the event and the drug is suspected or confirmed.

Sponsor assessment of expectedness and relationship to study drug/causality will determine the need for expedited reporting of AEs.

8.3 TIME PERIOD/FREQUENCY FOR EVENT ASSESSMENT/FOLLOW-UP

At every clinic visit, subjects will be assessed for AEs and SAEs. After the subject has had an opportunity to spontaneously mention any problems, the investigator should inquire about AEs by asking a non-leading question such as the following:

1. “How are you feeling?”
2. “Have you had any changes since your last assessment/visit?”
3. “Have you taken any new medicines since your last assessment/visit?”

8.3.1 POST-STUDY AE AND SAE

The investigator is not obligated to actively seek SAE information in former study subjects, but the investigator is encouraged to notify Alkahest, Inc. or their designee of any AE or SAE occurring within 30 days after a subject completes the study (or has their last visit) that the investigator judges may be reasonably related to study treatment or study participation.

8.4 REPORTING PROCEDURES

8.4.1 ADVERSE EVENT REPORTING

All subjects who have given informed consent will be evaluated for AEs. All AEs that occur after the time of treatment with the study agent will be considered Treatment Emergent AEs. Subjects with Treatment-Emergent AEs must be followed until the AE is resolved or is stable, unless the subject is lost to follow up.

Each AE or suspected adverse reaction must be described as follows: the date of onset, date of resolution, severity (mild, moderate, severe), frequency of the event (single episode, intermittent, continuous), action taken with study treatment (no action taken, treatment held, treatment discontinued), outcome, causality* (unrelated, possibly related, definitely related), and seriousness criteria. Each AE or suspected adverse reaction must be recorded separately.

***Note:** Causality assessment will be made only when the AE occurs after the subject has initiated at least one infusion of the study agent. An AE occurring before the subject’s exposure to study agent will always be labeled as “unrelated”.

Any AE occurring during the study must be documented in the subject’s medical records and as an AE in the

CRF. Any SAE occurring during the study must be documented in the subject's medical records and as an SAE in the CRF.

A separate set of SAE pages should be used for each SAE. However, if at the time of initial reporting, multiple SAEs are present that are temporally and/or clinically related, they may be reported on the same SAE page.

The investigator should attempt to establish a diagnosis of the event (that meets the definition of an AE or SAE) based on signs, symptoms, and/or other clinical information. In such cases, the diagnosis should be documented as the AE and/or SAE and not the individual signs or symptoms. The diagnosis will become the basis for the verbatim term as reported by the investigator. If no diagnosis is known and clinical signs and symptoms are not present, the abnormal finding should be recorded.

In addition to the investigator's own description of the AE, each AE will be encoded according to the MedDRA.

The investigator will take all appropriate and necessary therapeutic measures required for resolution of the AE, whether or not the AE is considered related to the investigational product. Any medication necessary for the treatment of an AE must be recorded on the concomitant medication CRF.

The SAE pages of the CRF should be completed as thoroughly as possible and signed by the investigator or his/her designee before transmittal to the study Contract Research Organization (CRO). It is very important that the investigator provide his/her assessment of causality to study drug as well as an applicable diagnosis at the time of the initial SAE report.

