Each infusion will be administered over approximately 30 minutes according to Stanford Hospital procedures for colloid infusions, but infusion rates and infusion time will be adjusted according to tolerability as determined by the anesthesiologist and infusion nurse. The infusion procedure of active and placebo agents will be identical to maintain the blind. The following measures will be taken to ensure adequate blinding during infusions: blinding of subjects, study coordinators, physicians, and raters to treatment allocation; use of unblinded infusion nurses; and measures to block view of the vial and drip chamber throughout the infusion.

Mass cytometry (CyTOF), a multiplexed, high-content immune profiling technology, will be used to provide high-resolution surveillance of circulating immune cells and the response to GRF6021 infusions on surgical recovery. Additional functional and quality of life assessments will be measured at baseline and approximately twice weekly for 6 weeks after hospital discharge.

Objectives: The primary objective of the study is to investigate the effect of GRF6021 on intracellular signaling cascades in blood leukocytes as determined by CyTOF. Secondary objectives include the effect of GRF6021 on clinical recovery parameters in patients undergoing primary hip or knee arthroplasty, safety and tolerability of GRF6021, and the effects of GRF6021 on plasma proteomics.

Endpoints: **Primary Endpoint:**

- Effect of GRF6021 on intracellular signaling cascades in blood leukocytes as determined by CyTOF.

Secondary Endpoints:

- Change from baseline in 3-Minute Diagnostic Interview for Confusion Assessment Method (3D-CAM).
- Time to 50% recovery of baseline value on the Surgery Recovery Scale (SRS).
- End of study treatment comparison of the Western Ontario and McMaster Universities Osteoarthritis Index (WOMAC)
- Time to a score of < 12/40 on a subset of questions from the WOMAC, Pain Subscale.
- Time to a score of < 18/60 on a subset of questions from the WOMAC, Physical Function Subscale.
- Change from baseline in the Short Form-36 (SF-36).
- Change from baseline in the Beck Depression Inventory-II (BDI-II).
- Opioid analgesic consumption during hospital stay and after discharge to end of study.
- Time to discharge.

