2.3 POTENTIAL RISKS AND BENEFITS

2.3.1 KNOWN POTENTIAL RISKS

GRF6021, a 5% human plasma protein fraction, is reduced in coagulation factors and gamma globulins and serves as a viable source of soluble, infusible plasma proteins from healthy male and female donors.

GRF6021 has been marketed since 1958 in the US, is approved in other parts of the world, and has a well-established safety profile with a very low frequency of reported infusion reactions (0.002%) ([PSUR](#)). Based on the cumulative review of post-marketing safety surveillance data ([PSUR](#)), the benefit-risk balance for GRF6021 as an investigative product in individuals undergoing THA or TKA is favorable. Because it has been depleted of the majority of immunogenic proteins, GRF6021 is not expected to alter the blood typing characteristics of the recipient and should not sensitize humans to its subsequent administration ([Bertrand 1959](#)). ABO antigen typing is not required prior to administration. Finally, the additional steps taken during production to remove viral pathogens provide an increased margin of pathogen safety in comparison to fresh frozen plasma.

GRF6021 is not expected to significantly alter safety laboratory parameters, including urinalysis, coagulation times, prothrombin times, prothrombin consumption, platelet counts, or fibrinogen levels when given in quantities of up to 1000 mL ([Bertrand 1959](#)). Hypotension may occur, particularly following rapid infusion. The blood pressure may normalize spontaneously after the slowing or discontinuation of the infusion. Vasopressors will also correct the hypotension ([PI](#)). GRF6021 is contraindicated for use in patients on cardiopulmonary bypass as severe hypotension has been reported ([Bland 1973](#)). GRF6021 is contraindicated in patients with severe anemia, congestive heart failure, or increased blood volume ([PI](#)).

GRF6021 is made from human plasma and may carry a risk of transmitting infectious agents, e.g., viruses, the variant Creutzfeldt-Jakob disease (vCJD) agent, and, theoretically, the Creutzfeldt-Jakob disease (CJD) agent. The risk that GRF6021 can transmit an infectious agent has been reduced by screening plasma donors for prior exposure, testing donated plasma, and including manufacturing steps with the capacity to inactivate and/or remove pathogens.

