4 STUDY DESIGN AND ENDPOINTS

4.1 DESCRIPTION OF THE STUDY DESIGN

This will be a randomized, placebo-controlled pilot study conducted at a single site, Stanford University (Stanford, California, US) to investigate the effects of GRF6021, a 5% human plasma protein fraction administered by intravenous (IV) infusion, on intracellular signaling cascades in blood leukocytes in subjects undergoing primary hip or knee arthroplasty.

Approximately 45 subjects will be enrolled with the aim of having 40 evaluable subjects randomized in a 1:1 ratio to active treatment or placebo. Each subject will receive 4 infusions of 250 mL of active GRF6021 or 4 infusions of 250 mL of placebo:

- 1) 1 infusion on the day before surgery
- 2) 1 infusion on the day of surgery within 4 hours before surgery start (first incision)
- 3) 1 infusion on the day of surgery upon arrival in the postoperative care unit (within 5 hours after the first incision)
- 4) 1 infusion on the day after surgery

Each infusion will be administered over approximately 30 minutes according to Stanford Hospital standard of care, but infusion rates and infusion time may be adjusted for tolerability or other clinical reasons, as determined by the anesthesiologist and infusion nurse.

CyTOF, a multiplexed, high-content immune profiling technology, will be utilized to provide high-resolution surveillance of circulating immune cells and the response to GRF6021 infusions on surgical recovery. Additional functional and quality of life assessments will be measured at baseline and for 6 weeks after hospital discharge. For a detailed overview of the timing of study assessments and interventions, please review [Section 15 Schedule of Events](#).

The overall duration of the study/recruitment period is approximately 12 months from study initiation (i.e., following consent of first subject) to study completion (i.e., last subject, last visit). The subject participation period is approximately 7 to 12 weeks from screening through end of study, unless prematurely discontinued.

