7.1.1.2.3 Vital Signs

Refer to [Section 7.1.1.1.4](#) for a description of vital signs. Vital signs will be collected at every treatment visit within 1 hour prior to infusion start and after infusion start, at 15, 30, 45, and 60 minutes (for further details see [Section 15 Schedule of Events](#)). Vital signs may be collected ad hoc during or after the infusion.

7.1.1.2.4 12-Lead ECG

A 12-lead ECG will be performed after the subject has rested quietly for at least 5 minutes in a supine or sitting position. In some cases, it may be appropriate to repeat abnormal ECGs to rule out technical factors contributing to ECG artifacts or abnormality. It is important that leads are placed in the same positions each time for consistency. The overall conclusion with the interpretation of the ECGs will be recorded on the appropriate CRF. The interpretation of the ECGs will be recorded as normal, abnormal but not clinically significant, or abnormal and clinically significant. Corrected QTc intervals will be calculated using Fridericia's correction formula.

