10.4.4 ADHERENCE AND RETENTION ANALYSES

Subject adherence with the study visit schedule, visit procedures, infusions, and subject retention will be assessed. Reasons for study discontinuation will be compared across groups and across other subgroups of subjects, as appropriate.

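### The adverse-event action-taken list has no category for a changed infusion rate, although the protocol provides for rate adjustment for tolerability

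*Protocol*

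**What the plan says.** Protocol section 8.4.1 lists what must be recorded for each adverse event. One item is "action taken with study treatment (no action taken, treatment held, treatment discontinued", and the list closes there.

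The protocol also describes how poor tolerability is handled during an infusion. The Protocol Summary states that "infusion rates and infusion time will be adjusted according to tolerability as determined by the anesthesiologist and infusion nurse". Section 4.1 uses permissive wording and a wider set of reasons: "infusion rates and infusion time may be adjusted for tolerability or other clinical reasons, as determined by the anesthesiologist and infusion nurse". Section 2.2 is close to section 4.1. Section 2.3.1 names the relevant risk, "Hypotension may occur, particularly following rapid infusion", and then says: "The blood pressure may normalize spontaneously after the slowing or discontinuation of the infusion".

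Safety and tolerability are a secondary objective (section 3). Section 10.4.4 plans that "Subject adherence with the study visit schedule, visit procedures, infusions, and subject retention will be assessed". The supplied SAP covers the primary endpoint, ActiGraph and proteomics. Its section 5 places the safety analyses in a separate SAP dated 08OCT2020, which was not available.

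**The concern.** The action-taken field should record what was done about a reaction. Here the response that the protocol itself provides for, a change of rate, has no code. Someone completing the form for a reaction managed by slowing must choose between *no action taken*, which is untrue, and *treatment held*, which describes something else.

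At stake is the tolerability comparison between arms. If one arm needed more rate changes, the field as written could not show it. A subject whose four infusions were all slowed but completed would look the same in that field as one who needed no adjustment. The infusion nurse is unblinded and takes part in rate decisions (Protocol Summary, section 6.1.5). A count by arm, with reasons, would therefore also show whether the arms were handled differently.

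**Working it through.** There is no figure in the plan to reproduce. The check sets the sections side by side.

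**1. Is the list closed?** The same sentence in section 8.4.1 gives severity and causality options in brackets, and these match the full sets in sections 8.2.1 and 8.2.2. The action-taken bracket has the same form, with no *other* and no *for example*. It reads as complete: 3 options, of which 0 cover a rate change.

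**2. Match responses to codes.**

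| Response | Where described | Fitting category |
|---|---|---|
| Infusion slowed, then completed | 2.3.1; rate and time adjustment in Summary, 2.2, 4.1 | none |
| Infusion discontinued | 2.3.1 | *treatment discontinued* |
| Infusion interrupted, then resumed | not described | *treatment held*, on a reasonable reading |
| Vasopressor given | 2.3.1 | concomitant medication record (8.4.1) |

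The clear gap is the first row.

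**3. Is the information named elsewhere?** Accountability records (6.2) cover receipt, dispensing and disposal. The perioperative variables (7.1.1.3.9) do not include duration of the study infusion. The safety summaries (10.4.3) cover laboratory values, vital signs, physical examination and ECG. The adherence analysis (10.4.4) mentions infusions without rate, duration or volume. The schedule of events (15.1) marks only that an infusion is given. No supplied section names rate or duration as a data item.

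**4. What is recorded regardless of this field?** Section 8.4.1 says "Any AE occurring during the study must be documented in" the medical records and the case report form, with onset, resolution, severity, outcome, causality and seriousness. Section 7.1.1.2.3 says "Vital signs will be collected at every treatment visit within 1 hour prior to infusion start and after infusion start, at 15, 30, 45, and" finally at one hour, with further readings as needed. The reaction and the blood pressure are therefore captured, and the missing part is the response.

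**5. Does duration matter for reading the vital signs?** Readings are timed from the start of an infusion that nominally lasts about 30 minutes. At 30 minutes' duration the 45- and 60-minute readings fall after the end. If an infusion is slowed to more than 45 minutes, the 45-minute reading falls during it; beyond 60 minutes, all four do. Actual duration is needed to know which case applies.

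**6. Scale.** SAP section 7.3 reports 37 evaluable subjects, each by definition with all 4 doses: 37 × 4 = 148 infusions. The split by arm is not given; if it were even, 148 / 2 = 74 per arm. The size of the safety set is not given either, so the table could be somewhat larger.

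**The case against.** The strongest reply is that only one attribute of a recorded event is affected. This stands. A reader might infer that slowing is the main sign of intolerance and that it goes unrecorded. The documents do not support that: no section calls slowing the main sign, and the signs themselves (the reaction and the blood pressure) are recorded whatever the action field allows. A reader might also infer that slowing hides harm in both the adverse-event and vital-sign summaries. That is conjecture. A reaction that prompts slowing comes before it and is reportable if it meets the definition in section 8.1.1, and blood pressure is read at four fixed times plus as needed. One limit on this reply is that abnormal assessments become adverse events only if clinically significant, so a brief fall reversed by slowing might not be reported as one. No list of actions would capture that case, since the field exists only within an adverse-event record.

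Second, the case report form, the Infusion Administration Manual and the 08OCT2020 SAP may capture rate or duration. This also stands, so nobody can say from these documents that the information is absent.

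Third, rate adjustment is permitted, so a slowed but completed infusion is compliant and the subject is properly evaluable. Agreed. Section 4.1 also allows adjustment for other clinical reasons, so raw duration would not isolate tolerability; the reason must be recorded as well.

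Fourth, the only frequency in the documents is low: 0.002% reported infusion reactions in section 2.3.1. That figure comes from post-marketing reports and does not count infusions slowed. It neither sizes the gap nor closes it.

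Fifth, enrollment has ended, so a new form category cannot collect data prospectively. This stands and shapes the fix.

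**Conclusion.** The point holds in a limited form. Read as written, section 8.4.1 would miscode an adverse event managed by slowing an infusion that was then completed, and the supplied documents name no other item that would recover the response. The event and the vital signs remain on record.

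The effect is minor. It touches the summary of tolerability, a secondary objective, and leaves the primary endpoint and the evaluable set unchanged. The number of infusions affected cannot be estimated, because the documents give no frequency of rate changes. The conclusion rests on two assumptions: that the bracketed list is complete, and that the unseen case report form, manual and safety SAP do not already record rate changes. If they do, the remaining defect is the coding list alone.

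**What to change.** In section 8.4.1, add *infusion rate reduced* to the action-taken list, and state that a temporary interruption is coded *treatment held*. In the safety analysis, report by arm the number of infusions slowed, interrupted or stopped, with the reason (tolerability or other) and the actual duration, taken from infusion records where these exist.

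For this trial the practical step is the table; the form category serves any further use of the protocol. If records of rate or duration turn out to be missing, the study report should say so and note that the action-taken field cannot show slowed infusions.

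The Summary says rates and times *will* be adjusted, while sections 2.2 and 4.1 say *may*. These should be reconciled so that the records are read against one rule. Which wording is right is not a matter for this review.

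The cost is one form category, one table and some abstraction from about 148 infusion records or slightly more. It needs no new procedure, staff or clinical rule.
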